## SERIOUS ADVERSE EVENTS

A "serious" AE (SAE) is defined as a significant clinical hazard, contraindication, or precaution that:

- Results in death
- Is life-threatening (In the opinion of the investigator, there is an immediate risk of death from the AE as it occurred. This does not include an AE that had it occurred in a more serious form may have caused death.)

- Results in a persistent or significant temporary disability/incapacity defined as a substantial disruption of a person's ability to conduct normal life functions
- Results in or prolongs an existing in-patient hospitalization (an overnight stay in the hospital, regardless of length) [Note: A hospitalization for an elective procedure or treatment which is not associated with an AE, hospitalization for a pre-existing condition which did not worsen, and hospitalization for reasons of convenience or observation, do not constitute an SAE.]
- Is a congenital anomaly/birth defect (in offspring of a subject taking the trial medication, regardless of time to diagnosis)
- Is an important medical event that may not result in death, be life-threatening, or require hospitalization but based upon the appropriate medical judgment, the event may jeopardize the subject and may require medical or surgical intervention to prevent one of the outcomes listed for the definition of a serious adverse experience.

The designated medical monitor will review all serious and unexpected adverse events associated with the protocol and provide an unbiased written report of the event within 10 calendar days of the initial report. At a minimum, the medical monitor will comment on the outcomes of the adverse event and relationship of the event to the Sonazoid administration. The medical monitor will also indicate whether he concurs with the details of the report provided by the principal investigator.

A copy of the SAE will be retained on file with the respective subject's data forms.

## 6.7 End-of-Treatment and End-of-Trial Evaluations

### 6.7.1 Discontinuation of Subjects

Subjects will be free to discontinue trial participation at any time. The investigator will also discontinue any subject from the trial if, in the investigator's opinion, it is not safe for the subject to continue. The date the subject is withdrawn from a treatment and/or from the trial and the reason for discontinuation will be recorded on the CRF. For portal hypertension patients that will be monitored by SHAPE for up to 18 months, the end point will be any one new complication (e.g., liver cancer) or a marked worsening in any complication (e.g., MELD scores) or the end of their clinical trial participation (up to 18 months). The time to reach the end point will be noted if a new complication or a marked worsening in any complication occurs. The time to reach the end point will be noted.

Trial participation will be considered completed if the subject has met all of the following trial

requirements:

- Has received at least one infusion of Sonazoid
- Has undergone the complete ultrasound imaging study as described in this protocol

If a subject's participation in the trial is interrupted for any reason (e.g., because of an AE or if the subject is lost to follow-up) and the subject has met the criteria described above for completing the trial, the subject's trial participation will be considered completed. If a subject's trial participation is interrupted for any reason by the subject's or investigator's choice and the subject has not met all of the criteria listed above, then the subject will be considered a discontinued subject.

## 7. DATA MANAGEMENT AND STATISTICAL ANALYSES

### 7.1 Data Management

Data forms will be completed for all subjects enrolled in the trial. The patient study files will be stored in a secure file cabinet and maintained by the research study coordinators at each institution (TJU and HUP). Patient study files will be kept for 7 years after the completion of the study. The PI of the study has previous experience running ultrasound clinical trials and will serve as the study sponsor. He will be responsible for ensuring all FDA requirements are met and all AE are properly reported.

The final data will be entered into a database. The investigator will be responsible for management of the database. The database will be maintained within an organized and secure directory system.

### 7.2 Statistical Analyses

#### 7.2.1 Hypotheses

$H_1$ : Can patients with HVPG of 10 mmHg or greater be identified using SHAPE? The fundamental hypothesis is that a sensitivity of 89% and a specificity of 81 % can be achieved by using SHAPE measurements to identify patients with HVPGs of 10 mmHg or greater.

H2: A correlation coefficient of 0.82 will be achieved between in vivo SHAPE and HVPG measurements.

H3: A correlation coefficients above 0.90 will be achieved between SHAPE and repeat HVPG results.

H4: SHAPE will significantly differentiate responders from non-responders using clinical outcomes as the reference standard.

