**Statistical Methodology:** This project is a large clinical trial to further develop SHAPE and to employ this method to conduct a large scale human clinical trial to conclusively establish the accuracy of SHAPE for the assessment of portal hypertension. Our statistical analysis will address following major questions:

1. Can patients with HVPG of 10 mmHg or greater be identified using SHAPE? The fundamental hypothesis is that a sensitivity of 89% and a specificity of 81 % can be achieved by using SHAPE measurements to identify patients with HVPGs of 10 mmHg or greater.
2. Can portal vein pressures (in the form of HVPGs) in patients with liver disease be quantified accurately using SHAPE? The fundamental hypothesis is that a correlation coefficient of 0.82 can be achieved between *in vivo* SHAPE and HVPG measurements.
3. Can SHAPE accurately monitor disease progression or treatment response in patients identified with portal hypertension? The fundamental hypothesis is that correlation coefficients above 0.90 can be achieved between SHAPE and repeat HVPG results and that SHAPE will significantly differentiate responders from non-responders (using clinical outcomes as the reference standard).

The findings of SHAPE will be correlated to the invasive catheter based measurements of portal vein blood pressure (i.e., HVPG) using least squares, multiple linear regression analysis with robust standard errors. Comparisons of sensitivities, specificities and accuracies for diagnosing portal hypertension with SHAPE will be conducted with an unpaired Student's t-test (using HVPG measurements as the reference standard). Receiver operating characteristic (ROC) curves will be computed using a continuous scale

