## 2. TRIAL OBJECTIVES

Trial Objectives: The primary objectives of this trial are:

- Evaluate the use of *in vivo* subharmonic aided pressure estimation (SHAPE) as a first qualitative screening modality for determining the presence of portal hypertension in patients undergoing a transjugular liver biopsy compared to catheter based pressure measurements (as the reference standard)
- Determine if SHAPE measurements can provide a quantitative, noninvasive measurement of hepatic venous pressure gradient (HVPG) to monitor disease progression or treatment response in patients identified with portal hypertension by comparing the results to repeat biopsies and/or clinical outcomes.

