### 7.2.3 Sample Size Calculation

As the most clinically important aim, the sample size analysis is based on specific aim 1 where each patient represents an independent entity. Based on our pilot study, the sensitivity and specificity of

SHAPE for the diagnosis of portal hypertension (i.e., HVPG > 10 mmHg) is 89% and 88%, respectively [Eisenbrey et al. 2013]. However, the confidence intervals achieved in the pilot study were (due to the limited sample size) very wide (worst case scenario: 52–100%). Hence, a power analysis was performed using NCSS/PASS 2008 (NCSS, East Kaysville, UT) to estimate the number of cases required to produce clinically acceptable 95% two-sided confidence intervals (for one correlation) [Newcombe 1998]. Table 2 below illustrates sample size calculations for the number of independent observations needed in the study population based upon 95% two-sided confidence intervals ranging from 0.06 to 0.10 for one correlation. A sample size between 259 and 278 subjects will provide 95% confidence intervals from 0.84 to 0.92 (i.e., a width of 0.08). A similar analysis was conducted based on the correlation between SHAPE and HVPG of 0.82 obtained in our pilot study [Eisenbrey et al. 2012a]. In that case to demonstrate that SHAPE can accurately measure HVPG values with a correlation coefficient of 0.82 requires between 264 and 343 patients (for confidence interval widths of 0.08 and 0.07, respectively). Hence, we selected a sample size for this study of 300 subjects.

Table 2: Sample size calculations for different 95% confidence intervals in the human clinical trial.

Target width	Proportion (R)	Lower limit	Upper limit	Sample size (N)
0.06	0.88	0.848	0.908	483
0.06	0.89	0.857	0.917	450
0.07	0.88	0.842	0.912	359
0.07	0.89	0.851	0.921	335
0.08	0.88	0.836	0.916	278
0.08	0.89	0.845	0.925	259
0.09	0.88	0.830	0.920	222
0.09	0.89	0.839	0.929	207
0.10	0.88	0.824	0.923	181
0.10	0.89	0.833	0.933	170

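### H2 tests only a correlation of 0.82, but the plan would read it as accurate measurement of HVPG; no error in mmHg is pre-specified

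*Combined protocol and SAP*

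**What the plan says.** The second question under Statistical Methodology in the Synopsis is: "Can portal vein pressures (in the form of HVPGs) in patients with liver disease be quantified accurately using SHAPE". The second objective in section 2 likewise aims at a quantitative, noninvasive measurement of HVPG. H2 in section 7.2.1 turns this into one criterion: "A correlation coefficient of 0.82 will be achieved between in vivo SHAPE and HVPG measurements". No null value, lower bound or error in mmHg goes with it.

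Section 7.2.3 bases the main sample size on aim 1 and then repeats the exercise for the correlation. It says that "to demonstrate that SHAPE can accurately measure HVPG values with a correlation coefficient of 0.82 requires between 264 and 343 patients". The smaller number goes with an interval 0.08 wide and the larger with one 0.07 wide, and the section settles on 300 subjects.

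For the analysis, sections 6.4 and 7.2.2 plan a least-squares multiple regression relating SHAPE to HVPG, with robust standard errors, and ROC curves at HVPG cut-offs of 10 and 12 mmHg. Neither section names mean bias, residual error, limits of agreement, a calibration check or a tolerable error as a result to be reported or judged.

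**The concern.** The question is about closeness in mmHg and the criterion is about linear association. These differ in two ways.

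- **Bias and scale.** Adding a constant to every SHAPE value, or multiplying every value by a positive constant, leaves r unchanged. A high r is therefore compatible with readings that are systematically too high or too stretched.
- **Case mix.** For a given size of measurement error, r rises with the between-patient spread of HVPG. H2 could be met or missed because of who was enrolled, with the accuracy of the technique unchanged.

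If r comes out near 0.82, the wording of section 7.2.3 ("to demonstrate that SHAPE can accurately measure HVPG values with a correlation coefficient of 0.82") invites the report that SHAPE measures HVPG accurately. A reader would then have no stated figure for how far an individual value may lie from the catheter value, and that is what the Synopsis question asks.

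**Working it through.** **Inputs from the documents**
- r = 0.82 (sections 7.2.1 and 7.2.3).
- 95% two-sided intervals, with N of 264 and 343 for widths 0.08 and 0.07, and 300 chosen (section 7.2.3).
- Cut-offs of 10 and 12 mmHg (section 7.2.2).
- An HVPG reduction of more than 20%, or to below 12 mmHg, linked to lower re-bleeding risk (section 1.1).

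**Input not in the documents**
- The between-patient SD of HVPG. I assume 4 to 7 mmHg and show 3 to 8.

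**1. The plan's own figure.** The Fisher interval for one correlation is tanh(atanh(r) ± 1.96/√(N − 3)), with atanh(0.82) = 1.157.
- N = 264: 0.776 to 0.856, width 0.08.
- N = 343: 0.782 to 0.852, width 0.07.
- N = 300: 0.779 to 0.854.

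The smallest N meeting each width is exactly 264 and 343, so the plan's arithmetic reproduces.

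**2. Error implied by r = 0.82.** After the best linear conversion of SHAPE to mmHg, the residual SD of HVPG is SD × √(1 − r²). Here r² = 0.672 and √(1 − 0.672) = 0.572. With normal errors of constant variance, the 95% half-width is 1.96 × 0.572 × SD and the median absolute error is 0.674 × 0.572 × SD.

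| Assumed SD of HVPG (mmHg) | Residual SD | 95% half-width | Median absolute error |
|---|---|---|---|
| 3 | 1.72 | 3.4 | 1.2 |
| 4 | 2.29 | 4.5 | 1.5 |
| 5 | 2.86 | 5.6 | 1.9 |
| 6 | 3.43 | 6.7 | 2.3 |
| 7 | 4.01 | 7.9 | 2.7 |
| 8 | 4.58 | 9.0 | 3.1 |

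**3. Cross-check by limits of agreement.** For two unbiased measures with equal SD, the half-width is 1.96 × SD × √(2(1 − 0.82)) = 1.96 × SD × 0.6. This gives 4.7 mmHg at SD 4 and 8.2 mmHg at SD 7, close to step 2.

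**4. Blindness to bias.** In a simulation of the equal-SD case, a constant shift of 3 mmHg left r at 0.82. The 95th percentile of absolute error moved from 4.7 to 6.9 mmHg at SD 4, and from 8.2 to 10.0 mmHg at SD 7.

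**5. Dependence on case mix.** Suppose SHAPE equals HVPG plus independent error. For r = 0.82 at SD 5, the error SD is 5 × √(1/0.6724 − 1) = 3.49 mmHg. Holding that error fixed:
- SD 4: r = 4/√(16 + 12.18) = 0.75.
- SD 7: r = 7/√(49 + 12.18) = 0.89.

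**6. Against the plan's own yardsticks.** The two cut-offs are 2 mmHg apart, and 20% of 12 mmHg is 2.4 mmHg. Even the smallest half-width in the table, 3.4 mmHg, exceeds both.

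**The case against.** The strongest reply is that H2 does not stand alone. Deciding whether a patient is above or below 10 mmHg is the task of H1, with ROC curves at 10 and 12 mmHg, and section 7.2.3 calls aim 1 the most clinically important and sizes the trial on it. That is correct, and nothing here weakens H1. But classification at a cut-off does not answer the separate question of quantification, which the Synopsis asks in its own right.

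A second reply is that the planned regression already yields slope, intercept and residual SD. That also stands: the analysis is not absent. What is absent is any statement that residual error will be reported or judged, and against what. Section 7.2.1 itself only claims a correlation; the accuracy wording is in the Synopsis and section 7.2.3.

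Third, the mmHg figures can be over-read. A reader might infer that SHAPE values will be wrong by 4.5 to 8 mmHg around the 10 mmHg cut-off. The documents do not support that:
- The figures are 95% limits, which about 5% of patients would exceed.
- They rest on an assumed SD of HVPG.
- They use one pooled residual SD, whereas the planned robust standard errors do not presuppose constant variance. Error near 10 mmHg could be smaller or larger.
- HVPG has its own measurement error, and SHAPE is done after the biopsy (within the 3-hour observation period, per the Synopsis), so not all of the scatter is SHAPE error.

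**Conclusion.** The concern holds in this form: the plan asks whether HVPG is quantified accurately, and its only criterion is a correlation that cannot show it. At r = 0.82, the 95% prediction half-width after perfect recalibration is about 4.5 to 7.9 mmHg for an assumed SD of HVPG of 4 to 7 mmHg, or 3.4 to 9.0 mmHg for 3 to 8. The corresponding median absolute error is about 1.5 to 2.7 mmHg for SD 4 to 7. These figures assume normal errors with constant variance and include the catheter's own error. An uncorrected bias or scale error would add to them without changing r.

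Confidence is high that the criterion is missing and lower on the mmHg range, because the SD is not in the documents. A reader might also infer that the sample size for H2 is wrong; it is not, since 264 and 343 reproduce exactly. The change should be made, but it does not affect H1 or the choice of 300 subjects.

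**What to change.** 1. In sections 7.2.1 and 7.2.2, keep r with its confidence interval as descriptive. Rest the H2 conclusion on error in mmHg: the cross-validated residual SD (RMSE) from regressing HVPG on SHAPE and the 95% prediction limits, each with a confidence interval, overall and for HVPG near 10 to 12 mmHg.
2. State in advance a tolerable error in mmHg, chosen and justified by the sponsor, against which these are judged. Without it H2 still has no decision rule.
3. Report mean bias, calibration slope and Bland-Altman limits only for a SHAPE-to-mmHg conversion fixed before the analysis, for example from the pilot data, or fitted at one site and tested at the other. With a line fitted to the same data, bias is near 0 and slope near 1 by construction, so they would say little.
4. If no tolerance is set, replace the accuracy wording in both the Synopsis (question 2) and section 7.2.3 with a statement that SHAPE correlates with HVPG.

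The cost is a few lines of text and a little more analysis of data already being collected, with no new patients or visits. The downside is that the result may read less favourably than a single r.

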### 7.2.2 Analysis of Results

The findings of SHAPE will be correlated to the invasive catheter based measurements of portal vein blood pressure (i.e., HVPG) using least squares, multiple linear regression analysis with robust standard errors. Receiver operating characteristic (ROC) curves will be computed using a continuous scale with HVPG cutoff levels of 10 and 12 mmHg. The optimal operating point (OOP) will be determined as the point closest to '0,1' on the ROC curve (representing 100% sensitivity and 100% specificity). All clinical variables (e.g., concomitant imaging results, presence of cancer or ascites, blood tests, fibrosis and MELD scores etc.) will also be compared to the SHAPE values. When both types of variables are ordinal or continuous, correlations will be calculated. When one type of variable is nominal and one continuous non-parametric rank order tests such as Mann-Whitney U-tests or Kruskal-Wallis tests will be performed [Rosner 1990]. All of the statistical analyses proposed for the human clinical trial will be repeated split by racial and ethnic groups to determine if clinically important race/ethnicity differences exist in the ability of SHAPE to diagnose portal hypertension.

All analyses and computations will be performed using NCSS/PASS 2008 and Stata 12.0 (Stata Corporation, College Station, TX), while the study database will be designed and implemented in Filemaker Pro 10.0 (Filemaker Inc, Santa Clara, CA). This database will contain all patient information (except names and other identifiers), including results of biopsies, HVPG and SHAPE measurements as well as the clinical variables.

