#### 6.4 Efficacy Assessments

The findings of SHAPE will be correlated to the invasive catheter based measurements of portal vein blood pressure (i.e., HVPG) using least squares, multiple linear regression analysis with robust standard errors. Comparisons of sensitivities, specificities and accuracies for diagnosing portal hypertension with SHAPE will be conducted with an unpaired Student's t-test (using HVPG measurements as the reference standard). Receiver operating characteristic (ROC) curves will be computed using a continuous scale with HVPG cutoff levels of 10 and 12 mmHg. The optimal operating point (OOP) will be determined as the point closest to '0,1' on the ROC curve (representing 100% sensitivity and 100% specificity). All clinical variables (e.g., concomitant imaging results, presence of cancer or ascites, blood tests, fibrosis and MELD scores etc.) will also be compared to the SHAPE values.

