The Interventional Radiology Divisions at Thomas Jefferson University (TJU) and the Hospital of the University of Pennsylvania (HUP) performs approximately 85 and 100 transjugular liver biopsy procedures with pressure measurements per year, respectively. The patient population of this project will reflect the population demographics found at major American urban academic health centers. The overall hospital demographics for TJU and HUP include 66% Caucasian, 30% African American, and 4% Asian, with 10% representing Hispanic patients. The goal is to enroll 300 patients over the last 3 years of this project, which means we are aiming for a recruitment rate of approximately 54%.

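### The SHAPE cut-off is chosen as the ROC point closest to (0,1) with no optimism correction planned, so sensitivity and specificity read there in the same patients are overstated, by about 1-2 points for most case mixes at N=300

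*Combined protocol and SAP*

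**What the plan says.** H1 (7.2.1) is that "a sensitivity of 89% and a specificity of 81 % can be achieved by using SHAPE measurements" for patients with HVPG of 10 mmHg or greater. Section 6.4 and the Synopsis add: "Comparisons of sensitivities, specificities and accuracies for diagnosing portal hypertension with SHAPE will be conducted". Neither statement gives a SHAPE threshold.

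The one rule that yields a threshold stands in the Synopsis, 6.4 and 7.2.2: "The optimal operating point (OOP) will be determined as the point closest to '0,1' on the ROC curve". ROC curves are planned for two HVPG reference levels, 10 and 12 mmHg, so there are two such operating points.

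Section 7.2.3 reports that in the pilot the sensitivity and specificity of "SHAPE for the diagnosis of portal hypertension (i.e., HVPG > 10 mmHg) is 89% and 88%, respectively", without the SHAPE cut-off behind those figures. It sets the sample size as the number of cases "required to produce clinically acceptable 95% two-sided confidence intervals".

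Section 7.2.2 also says: "All of the statistical analyses proposed for the human clinical trial will be repeated split by racial and ethnic groups". It does not say whether the operating point is then chosen afresh in each group. No split sample, cross-validation, bootstrap or outside validation set is described anywhere.

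**The concern.** The rule is prespecified, but the number it produces is not: it comes from the data. Choosing the point nearest the ideal corner of an empirical ROC curve favours a cut-off at which chance has helped. If sensitivity and specificity are then read at that cut-off in the same patients, both exceed on average what the same cut-off would achieve in new patients. The excess is larger for the measure estimated from fewer patients.

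The trial is meant "to conclusively establish the accuracy of SHAPE for the assessment of portal hypertension", and 7.2.3 treats the diagnostic aim as the most important one clinically. The reported accuracy and its interval are therefore the main product. H2 and H3 are correlations, need no cut-off and are not affected.

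**Working it through.** **1. The plan's own figures.** All ten rows of Table 2 in 7.2.3 reproduce with the exact (Clopper-Pearson) interval. With x = np, the limits are the 0.025 quantile of Beta(x, n-x+1) and the 0.975 quantile of Beta(x+1, n-x). For p = 0.88, n = 278 this gives 0.836 to 0.916; for p = 0.89, n = 259 it gives 0.845 to 0.925. This interval treats the cut-off as fixed.

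**2. Inputs.** From the documents: N = 300 (7.2.3), 89%/81% (7.2.1) and the closest-to-(0,1) rule (7.2.2). Assumed: normal SHAPE scores with equal SD in the two HVPG classes, and a prevalence of HVPG of at least 10 mmHg of 20-80%.

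**3. Curve.** Separation d' = z(0.89) + z(0.81) = 1.227 + 0.878 = 2.104 (from unrounded z values). The curve is symmetric, so its point closest to (0,1) has sensitivity = specificity = Φ(2.104/2) = Φ(1.052), about 85.4%. The rule therefore aims at about 85%/85%, not at 89%/81%.

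**4. Overstatement.** In each simulated trial the cut-off c* minimises (1-Se)² + (1-Sp)² on the empirical curve. Overstatement is the observed value at c* minus the true value at c*. Means over 5,000 trials per row, in %; differences are from unrounded values:

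| Prevalence | HVPG ≥10 / <10 | Observed Se/Sp | True Se/Sp at c* | Overstatement Se/Sp |
|---|---|---|---|---|
| 20% | 60/240 | 87.0/86.5 | 84.3/85.9 | +2.7/+0.7 |
| 30% | 90/210 | 86.6/86.5 | 84.6/85.7 | +2.0/+0.8 |
| 40% | 120/180 | 86.5/86.3 | 85.0/85.4 | +1.5/+1.0 |
| 50% | 150/150 | 86.4/86.4 | 85.2/85.2 | +1.2/+1.2 |
| 60% | 180/120 | 86.3/86.4 | 85.3/85.0 | +1.0/+1.4 |
| 70% | 210/90 | 86.4/86.7 | 85.5/84.8 | +0.8/+1.9 |
| 80% | 240/60 | 86.5/86.9 | 85.9/84.3 | +0.7/+2.7 |

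**5. Other models.** A curve through the pilot's 89%/88% gives +0.6 to +2.4 for single measures. SD ratios of 1.5 and 2 (prevalence 30% and 50%) give a mean of the two measures of 1.1 to 1.3. A bivariate normal model with r = 0.82 gives +2.9/+0.7, +1.9/+1.2 and +1.2/+1.5 at 20%, 40% and 60%.

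**6. Intervals.** Exact 95% intervals for sensitivity, 12,000 simulated trials per column:

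| Prevalence | 20% | 35% | 50% | 60% |
|---|---|---|---|---|
| Overstatement (points) | 2.6 | 1.7 | 1.2 | 1.0 |
| Mean interval width (points) | 18.3 | 13.8 | 11.5 | 10.5 |
| Lower bound above truth, chosen cut-off | 4.8% | 4.6% | 4.1% | 4.3% |
| Lower bound above truth, fixed cut-off | 1.8% | 2.3% | 2.0% | 1.5% |
| Upper bound below truth, chosen cut-off | 0.2% | 0.5% | 0.5% | 0.8% |

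The overstatement is about 10-14% of the width (2.6/18.3 = 14%; 1.0/10.5 = 10%). Total misses are 4.6-5.1% (for example 4.8 + 0.2 = 5.0), so coverage is kept but the two tails are unequal.

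**7. Subgroups, only if the cut-off is re-derived.** Section 7.2.3 gives hospital demographics of "66% Caucasian, 30% African American, and 4% Asian, with 10% representing Hispanic patients". Applied to 300, 66% is 198, 30% is 90 and 4% is 12; these are not enrolment forecasts. With identical true accuracy, observed sensitivity plus specificity averages 1.4-2.2 points higher at n = 90 than at n = 198. With one overall cut-off the gap is within about 0.2 points of zero. At 40% prevalence the overstatement is +3.2/+2.0 at n = 90 and about +12/+8 at n = 12.

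**The case against.** The strongest reply is that this is minor beside sampling error, and much of that stands. In simulation sensitivity was not overstated in 29-35% of trials. The correction lowers its root mean squared error only from 5.35/3.80/3.09/2.83 to 4.87/3.55/2.86/2.69 points at 20/35/50/60% prevalence, a gain of 5-9%. The plan names no interval method for the analysis itself. The exact interval used here is the one that reproduces Table 2, and its conservatism explains why the fixed cut-off misses below the nominal 2.5%.

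It is also fair to say that reading accuracy at the operating point in the same patients is inferred. The plan does not state it outright, but it names no other source for the curve and no other cut-off.

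A reader might infer that the bias helps the trial to meet H1. The documents do not support that. H1 has no null value, lower-bound rule or success criterion. Under the assumed curve, mean observed sensitivity at the operating point is 86.3-87.0%, below 89%, while specificity is 86.3-86.9%, above 81%. That shift comes from where the rule sits on the curve and is larger than the optimism.

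A reader might also infer that the subgroup results will be distorted. That holds only if the cut-off is re-derived in each group, which the plan leaves open.

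What survives is that the bias runs in one direction on average, favours SHAPE, and can be largely removed without new data.

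**Conclusion.** The concern holds as a modest, correctable bias in the reported accuracy. At N = 300 sensitivity and specificity at the chosen cut-off are overstated by about 1-2 points for most splits. The figure rises to about 2.5-3 points for whichever measure rests on the smaller group: sensitivity at 20% prevalence, specificity at 80%. The size rests on the binormal model and on a prevalence that the documents do not give; the other models tried lead to a similar range.

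It would go too far to say that the intervals fail, since total coverage stays near 95% and only the balance of misses shifts towards SHAPE. No pass/fail decision turns on it. The change is worth making because it is cheap, but the trial does not stand or fall by it.

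**What to change.** Add to 7.2.2:

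> For each HVPG cut-off (10 and 12 mmHg), sensitivity and specificity at that cut-off's OOP will be corrected for optimism by bootstrap. Patients are resampled, the OOP is re-selected in each resample and applied to the original data, and the mean difference (resample value minus original-data value) is subtracted from the apparent value. The 95% CI is shifted by the same amount and labelled approximate. Corrected values are reported as the H1 estimate beside the apparent values. Race/ethnic groups are analysed at the overall OOP for each HVPG cut-off, not at a re-derived one.

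Cross-validation is an acceptable alternative. The cost is a paragraph and a short program, with no new patients or data.

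In simulation at 20/35/50/60% prevalence, reported sensitivity falls by 1.8/1.2/0.9/0.7 points and specificity by 0.5/0.6/0.9/1.1. About a third of the bias remains (sensitivity +0.8/+0.5/+0.4/+0.3). The rate at which the lower bound for sensitivity lies above the truth falls from 4.0-4.6% to 2.5-2.7%, and the opposite miss rises from 0.4-0.7% to 1.6-1.8%, so the tails are close to balanced. The shifted interval ignores the uncertainty in the estimated optimism, hence the label approximate.

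### The plan's only ROC cut-off rule, the point closest to (0,1), is not tied to H1's pair of 89% sensitivity and 81% specificity and does not test it

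*Combined protocol and SAP*

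**What the plan says.** Section 7.2.1 (H1) and the synopsis give the target: "a sensitivity of 89% and a specificity of 81 % can be achieved by using SHAPE measurements to identify patients with HVPGs of 10 mmHg" or more.

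Section 7.2.2 plans the curve: "Receiver operating characteristic (ROC) curves will be computed using a continuous scale with HVPG cutoff levels of 10 and 12 mmHg". It then gives one rule for choosing a point on it: "The optimal operating point (OOP) will be determined as the point closest to '0,1' on the ROC curve". The same rule stands in the synopsis (Statistical Methodology) and in section 6.4. No SHAPE threshold is fixed in advance, and no rule holds sensitivity or specificity at a target value. The synopsis and section 6.4 also mention an unpaired t-test on sensitivities and specificities, but name no cut-off for it.

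Section 7.2.3 sizes the trial on a different pair. It says that the pilot sensitivity and specificity of "SHAPE for the diagnosis of portal hypertension (i.e., HVPG > 10 mmHg) is 89% and 88%, respectively". The 300 subjects are justified by the width of 95% confidence intervals. No success criterion for H1 is given.

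**The concern.** H1 is a statement about one location on the ROC curve: specificity 81%, sensitivity 89%. The closest-to-(0,1) rule minimises (1 - sensitivity)² + (1 - specificity)², which weighs both errors alike and makes no reference to that location. It will generally report a different pair, so the number produced does not answer the question that H1 asks.

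Section 7.2.3 calls this aim the most clinically important one, and section 2 describes SHAPE as a "first qualitative screening modality for determining the presence of portal hypertension". If the closest point is the only pair reported, a test with exactly the claimed performance would tend to show sensitivity below the claim and specificity above it. If some other point is used, the plan does not say which, so it could be chosen after the data are seen.

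**Working it through.** **Inputs from the documents.** H1 pair 0.89/0.81 (7.2.1); closest-to-(0,1) rule (7.2.2); pilot pair 0.89/0.88, Table 2 and N = 300 (7.2.3).

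**Assumptions not in the documents.** Binormal ROC shape with slope b, and the prevalence of HVPG of 10 mmHg or more.

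**1. The plan's own figures.** Take the smallest n whose exact (Clopper-Pearson) two-sided 95% interval for one proportion is no wider than the target. This reproduces all ten rows of Table 2. For width 0.08, p = 0.88 needs n = 278 (0.836 to 0.916) and p = 0.89 needs n = 259 (0.845 to 0.925). The sizing is therefore about precision at 88-89%. The plan states no figure for the pair expected at the closest point.

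**2. Where the rule lands if H1 is exactly true.** The curve is sensitivity = Φ(a + b·z(FPR)), where FPR = 1 - specificity. Forcing it through FPR 0.19 and sensitivity 0.89 gives a = z(0.89) + b·z(0.81).

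For b = 1, a = 2.104 and the AUC is Φ(2.104/√2) = 0.932. The curve is symmetric, so the closest point has sensitivity = specificity = Φ(2.104/2) = 0.854. Its distance to (0,1) is √(0.146² + 0.146²) = 0.207. At H1's own point the distance is √(0.11² + 0.19²) = 0.220, so the rule prefers 85.4/85.4.

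Minimising the distance numerically for other slopes through the same 89/81 point:

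| b | Sensitivity at closest point | Specificity at closest point |
|---|---|---|
| 0.6 | 84.8% | 88.7% |
| 0.8 | 85.0% | 86.8% |
| 1.0 | 85.4% | 85.4% |
| 1.25 | 86.0% | 84.0% |
| 1.5 | 86.7% | 83.0% |
| 2.0 | 87.9% | 81.7% |

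The sensitivity shortfall runs from 89 - 87.9 = 1.1 to 89 - 84.8 = 4.2 points. The closest point coincides with 89/81 only at b of about 2.5. A symmetric bilogistic curve gives 85.5/85.5, and two power-law curves give 84.8/90.5 and 88.0/81.6.

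**3. What N = 300 would show.** Empirical ROC curves were simulated with the true curve through 89/81, prevalence 20-60%, and b of 0.7, 1.0 and 1.3.
- Mean sensitivity at the closest point was about 86-88%.
- Both point estimates reached 89/81 at the closest point in about 12-30% of trials.
- Some point on the same empirical curve reached both in about 44-57%. A figure near one half is expected, because the true curve only just passes through the target.
- In a further set (prevalence 20-50%, b 0.8-1.25), the upper Clopper-Pearson 95% limits at the closest point reached both 89% and 81% in about 79-98% of trials.

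With prevalence 35% and b = 1, the chance that the closest point meets both falls to about 5% at N = 1000 and below 1% at N = 3000. Those sizes are not this trial. They show only that the shift comes from the rule and not from sampling error.

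**4. If the true pair is the pilot's 89/88.** With b = 1, a = z(0.89) + z(0.88) = 2.402, and the closest point is Φ(1.201) = 88.5/88.5. The shortfall is then half a point.

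**The case against.** The strongest reply is that nothing in the documents says H1 is judged at the closest point. H1 says that the pair can be achieved, which is a claim about the curve, and the plan will compute the whole curve. This stands, and it rules out the inference that a SHAPE test performing exactly as claimed would be reported as failing. There is no pass/fail rule on point estimates, and at N = 300 the upper 95% limits usually reach both targets.

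Three further points also stand.
- A reader might infer that the rule always returns a balanced 85/85. It returns the nearest point, which is balanced only on a symmetric curve, and the documents do not assume one.
- A reader might take 89/81 as a deliberate sensitivity-first trade for screening. The documents never explain the 81%, and the nearly balanced 89/88 used for sizing fits that reading poorly.
- No participant is missed because of the rule, since portal hypertension is identified here by HVPG and not by SHAPE.

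One objection to the remedy does not defeat it. Choosing the cut-off so that sensitivity is 89% does make the sensitivity half true by construction. But a claim that the curve reaches a given point is tested by fixing one coordinate and estimating the other. Specificity at 89% sensitivity does this directly; the closest point does not. The interval must allow for the cut-off being estimated.

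**Conclusion.** The concern holds in a limited form. The only stated operating-point rule is not tied to H1's pair and does not test it, and the plan names no other point or criterion for H1. If the true curve passes through 89/81 and is binormal with slope 0.6 to 2, the rule reads sensitivity at about 85-88% and specificity at about 82-89%, a sensitivity shortfall of 1 to 4 points. The direction was the same for every binormal slope tried below about 2.5. The size depends on curve shape, and the simulated frequencies also depend on prevalence; the documents give neither. The gap almost vanishes at 89/88.

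The documents do not support the stronger conclusion that the trial would reject or fail H1 because of this rule. This is a modest improvement to make before the data are seen, not a must-fix.

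**What to change.** In section 7.2.2, and in the matching text of the synopsis (Statistical Methodology) and section 6.4:

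1. State that H1 is evaluated as the specificity at 89% sensitivity on the ROC curve for HVPG of 10 mmHg or more, compared with 81%.
2. Report a 95% confidence interval that allows for the cut-off being estimated in the same data, for example by bootstrapping the whole procedure.
3. State openly that sensitivity is fixed by construction in this reading.
4. Keep the closest-to-(0,1) point as a secondary description.
5. Reconcile the 81% specificity in H1 with the 88% used in section 7.2.3, or explain the difference.

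The cost is wording and a short bootstrap routine, with no extra patients, visits or measurements. The downside is that the headline specificity will usually be lower than at the closest point.
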